PROTOCOL TITLE

Open-Label Prospective Randomized Control Trial to Investigate the Efficacy of Omega-3 Fatty Acid Therapy in Preventing Gastrointestinal Bleeding in Patients with Continuous-Flow Left Ventricular Assist Device

Version: 05Jun2019

NCT03784963

PROTOCOL TITLE

Open-Label Prospective Randomized Control Trial to Investigate the Efficacy of Omega-3 Fatty Acid Therapy in Preventing Gastrointestinal Bleeding in Patients with Continuous-Flow Left Ventricular Assist Device

PRINCIPAL INVESTIGATOR

[name]
Department of Medicine, Section of Cardiology
[contact]

OBJECTIVES

Aim 1: We will evaluate whether high-dose omega-3 fatty acid (O3FA) supplementation alters markers of angiogenesis and inflammation in patients with continuous-flow left ventricular assist devices (CF-LVAD).

- **Aim 1a** will assess the effect of high-dose O3FA in patients who have not experienced an episode of gastrointestinal (GI) bleeding. Patients will be enrolled up to 3 months following CF-LVAD implantation and randomized to high-dose O3FA or none. Markers of angiogenesis and inflammation will be assessed prior to and following initiation of high-dose O3FA therapy.
- **Aim 1b** will assess the effect of high-dose O3FA in CF-LVAD patients who have already experienced a GI bleeding event. Patients who have experienced a prior bleeding event will be enrolled and randomized to high-dose O3FA or none. Markers of angiogenesis and inflammation will be assessed prior to and following initiation of high-dose O3FA therapy.

Aim 2: We will assess the changes that occur to the microbiome of CF-LVAD patients following O3FA supplementation.

Aim 3: We will assess the effect of high-dose O3FA supplementation on GI bleeding events in both the population without prior GI bleeding events, and the population with prior GI bleeding events.

BACKGROUND

Continuous-flow left ventricular assist devices (CF-LVAD) have become the mainstay of therapy for advanced heart failure, both as bridge to transplantation and as destination therapy, allowing significant improvement in survival. However, this therapy is limited by a high adverse event profile, specifically those related to hemocompatibility.

One of the leading causes for readmission after CF-LVAD implantation is gastrointestinal (GI) bleeding, representing nearly 30% of both early and late readmissions following device implantation¹. Multiple reports found that 25-40% of the patients will experience GI bleeding, with 15.9% in the first 6 months in the MOMENTUM 3 trial, and 35.1% in the ENDURANCE trial^{2, 3}. Originally, pathophysiology of GI bleeding was attributed to Von Willebrand factor deficiency^{4, 5}. More recently, focus has shifted to the development of arteriovenous malformations (AVMs) in the GI tract as a major contributor to the development of GI bleeding in patients supported with CF-LVADs⁶.

The process of angiogenesis is controlled by angiopoietins 1 and 2 (Ang-1 and Ang-2), and vascular endothelial growth factor (VEG-F). Ang-1 leads to normal angiogenesis in conjunction with VEG-F, while Ang-2 promotes dysfunctional vessel growth with an expression that is highly regulated by the thrombin receptor PAR-1. Our group recently demonstrated that an abnormal ratio of Ang-1 and Ang-2 has a key role in abnormal angiogenesis, due to elevated Ang-2 and reduced Ang-1⁷. CF-LVAD patients with Ang-2 levels above the mean had more nonsurgical bleeding events compared to those with levels below the mean⁷. Furthermore, we found that tumor necrosis factor- α (TNF- α) was significantly higher in serum of patients with CF-LVAD compared to patients with heart failure or heart transplantation, and contributes to abnormal angiogenesis by killing pericytes and reducing Ang-1 levels⁸. We have confirmed these findings in a larger cohort from the PREVENT biobank. 114 paired samples obtained before and 3 months after CF-LVAD implantation were analyzed. 69% of patients with increased levels of Ang-2 and TNF- α experienced significant GI bleeding 6 months after implantation while only 38% of patients with Ang-2 and TNF- α levels below the mean had GI bleeding ($p=0.02$).

To further implicate the role of dysregulated angiogenesis in GI bleeding in CF-LVAD patients, Houston et al. evaluated the use of angiotensin-converting enzyme inhibitor (ACEI) and angiotensin receptor blocker (ARB) therapy in reducing the risk of GI bleeding. Ang-2 expression has previously been shown to be induced through angiotensin II signaling⁹. Houston et al showed that of the patients who did not receive angiotensin II antagonism, 48% experienced GI bleeding. In contrast, only 24% of the patients who received ACEI or ARB experienced GI bleeding¹⁰.

In the most recent J-MACS (Japanese registry for Mechanically Assisted Circulatory Support registry) report, GI bleeding occurred in 4 of 259 patients followed during a 5-year period¹¹. This is in stark contrast to the latest INTERMACS update that reports a rate of 16.24 events of GI bleeding per 100 patient months in the first 3 months after implantation, and 4.08 events per 100 patient months in the 3-12 months after implantation¹². What accounts for this difference? One possibility may lie in the Japanese diet, which is rich in omega 3 fatty acids (O3FA) compared to the diet of patients in the United States. We performed a retrospective study in a cohort of 166 patients with CF-LVAD to assess this theory. Patients who received high-dose O3FA as part of a recovery protocol were compared to those who did not. The frequency of GI bleeding was significantly lower in the O3FA group compared with the control group (0.077 ± 0.419 events/year vs. 0.305 ± 0.847 events/year, $p = 0.033$), leading to a higher 1-year event-free rate in the O3FA group compared to the control group (97% vs. 79%, $p = 0.046$).

In the past decade, there has been an emergence of interest in the human gut microbiota. Using next-generation sequencing (NSG), studies have been able to characterize with great detail the gut microbiome in humans. Further studies have shown that the microbiota is affected by patient characteristics (age, sex, body mass index, lifestyle), diet, and pathologic diseases¹³. In particular, O3FA and its effect on the gut microbiota has been studied, showing that an increase in dietary or supplemental O3FA changes the fingerprint of the microbiome¹⁴⁻¹⁶. O3FA and the microbiome also have a presence in the cancer literature. It is postulated that O3FA play a role in the prevention and treatment of cancer by reduction in cell proliferation, cell survival, angiogenesis, and inflammation¹⁷.

The data presented thus far shows a possible link between O3FA, GI bleeding, and abnormal angiogenesis, and may be related to the microbiome in CF-LVAD patients. This prospective randomized study aims to evaluate the effect of supplemental O3FA on the frequency of GI bleeding in patients implanted with CF-LVAD both as primary and secondary prevention.

Additionally, we will investigate the effect of O3FA on angiogenesis parameters (Ang-1, Ang-2, VEGF, TNF- α) and the microbiome.

STUDY ENDPOINTS

The primary endpoint will be a change in angiogenesis markers resulting in dysregulated angiogenesis, as described above. Secondary endpoints include rate of GIB and improvement in inflammatory markers.

STUDY INTERVENTION

The study intervention being evaluated is high-dose O3FA (4,000 mg), which is an over-the-counter supplement. Heart failure patients are routinely instructed to take an O3FA supplement for heart health. The research team will fund the supplement, which will be stored in the heart failure office. Once a patient is enrolled, a total of 1 year of supplement will be given to the patient for consumption at home.

PROCEDURES INVOLVED

We will perform an open-label, prospective, randomized control study in which 120 CF-LVAD patients are enrolled. We plan to have 2 separate arms: primary prevention and secondary prevention (60 in each arm). In the primary prevention arm, 60 patients who have received CF-LVAD implantation and have not experienced any episodes of GI bleeding will be assigned to an O3FA group or a control group, with 30 patients in each group. In the secondary prevention arm, 60 LVAD patients who have experienced at least 1 episode of GI bleeding after CF-LVAD implantation will be assigned to an O3FA group or a control group, with 30 patients in each group. Randomization will be performed using computer software, and initiation of therapy will start within 24 hours of randomization. O3FA will be given at a dose of 4,000 mg orally per day, and all patients will receive guideline-directed medical therapy during the study period.

The following study procedures will be performed:

Baseline

Subject to sign consent
Verify inclusion/exclusion criteria
Record medical history and medications
Collect stool sample
Collect blood sample
Randomization
For O3FA subjects:
-Provide O3FA supplement
-Subjects will be instructed to take 4 pills a day

1.5 months post-randomization

Record medical history and medications
Record adverse events
For O3FA subjects:
-Provide O3FA supplement
-Subjects will be instructed to take 4 pills a day
-Study drug compliance check

3 months post-randomization

Record medical history and medications

Collect stool sample

Collect blood sample

Record adverse events

For 03FA subjects:

- Provide O3FA supplement

- Subjects will be instructed to take 4 pills a day

- Study drug compliance check

4.5 months post-randomization

Record medical history and medications

Record adverse events

For 03FA subjects:

- Provide O3FA supplement

- Subjects will be instructed to take 4 pills a day

- Study drug compliance check

6 months post-randomization

Record medical history and medications

Collect stool sample

Collect blood sample

Record adverse events

For 03FA subjects:

- Provide O3FA supplement

- Subjects will be instructed to take 4 pills a day

- Study drug compliance check

7.5 months post-randomization

Record medical history and medications

Record adverse events

For 03FA subjects:

- Provide O3FA supplement

- Subjects will be instructed to take 4 pills a day

- Study drug compliance check

9 months post-randomization

Record medical history and medications

Record adverse events

For 03FA subjects:

- Provide O3FA supplement

- Subjects will be instructed to take 4 pills a day

- Study drug compliance check

10.5 months post-randomization

Record medical history and medications

Record adverse events

For 03FA subjects:

- Provide O3FA supplement

- Subjects will be instructed to take 4 pills a day

- Study drug compliance check

1 year post-randomization

Record medical history and medications

Collect stool sample

Collect blood sample

Record adverse events

For O3FA subjects:

-No more O3FA supplements will be provided by the study

-Study drug compliance check

Stool Collection for Microbiome Sequencing Analysis

Stool will be collected in the hospital prior to CF-LVAD implantation, as most patients have prolonged hospitalizations prior to implantation. Additional stool samples will be collected at home after CF-LVAD implantation at 3 months, 6 months, and 1 year. Stool samples will be collected using home stool sample kits. The stool will be kept cool in anaerobic conditions and will be shipped directly to [name] laboratory at the University of Chicago for microbiome analysis. For whole stool samples, we will employ the BioCollector at home stool sampling kit (BioCollective, Denver CO, USA). Smaller stool samples will be collected using a non-invasive double-tipped sterile polyester culture swabs (Becton-Dickinson catalog # BD 220135). All samples will be shipped straight to [name] lab for aliquot and storage at -80C until DNA extraction of microbiome samples. Microbiome DNA will be isolated with the MoBio Powersoil kit with the addition of mechanical lysis. DNA samples will be subsequently quantified by Quant-iT PicoGreen dsDNA Assay (Life Technologies) and normalized to a concentration of 50 pg/mL. Whole-genome shotgun sequencing libraries will be prepared according to the manufacturer's instructions using the Nextera XT DNA Library Preparation kit (Illumina) with 100-250 pg input DNA. Libraries will be pooled by transferring equal volumes of each library using a Labcyte Echo 550 liquid handler. The concentrations and insert size ranges for each pooled library will be checked using an Agilent Bioanalyzer DNA 1000 kit (Agilent Technologies). Libraries will be subsequently sequenced on the Illumina HiSeq 2500 platform in paired-end mode (2x151bp) targeting ~10Gb of sequences per sample.

Blood Collection

Complete metabolic panel including liver function tests, complete blood count, lipid profile, and inflammatory markers (hs-CRP and ESR) will be collected as standard of care. Approximately 20mL of peripheral blood will be collected and tested for markers of angiogenesis using a multiplex immunoassay system (Biorad). The angiogenesis factors to be measured are angiopoietin-2, epidermal growth factor (EGF), endoglin, sCD40L, vascular endothelial growth factor A, C and D, (VEGF-A, -C, -D), placental growth factor (PIGF), heparin-binding EGF-like growth factor (HB-EGF), plasminogen activator inhibitor-1 (PAI-1), insulin-like growth factor binding protein (*IGFBP*)-1, transforming growth factor alpha (TGF- α), and urokinase-type plasminogen activator (uPA). The inflammatory markers to be measured are Interleukin-6 (IL-6), Interleukin-8, Interleukin-18 (IL-18), sCD40L, soluble Fas ligand (sFASL), and TNF α .

Data will be collected from the subjects' medical records for up to 2 years post-randomization to collect outcomes and adverse events.

GIB episodes will be defined by INTERMACS:

An episode of SUSPECTED INTERNAL OR EXTERNAL BLEEDING that results in 1 or more of the following:

1. Death
2. Re-operation
3. Hospitalization
4. Transfusion of red blood cells as follows:
 - During first 7 days post implant (≥ 4 units packed red blood cells within any 24-hour period in patients $\geq 50\text{kg}$ or $\geq 20\text{cc/kg}$ packed red blood cells within any 24-hour period in patients $< 50\text{kg}$)
 - After 7 days post implant (transfusion of packed red blood cells (PRBC) after 7 days following implant with the investigator recording the number of units given.)

During the 1-year study period, clinical events including GIB and other major adverse events will be recorded and evaluated on a regular basis.

DATA AND SPECIMEN BANKING

Peripheral blood collected from consented participants will be stored in refrigerators at -80C for the duration of the study. All members of the research team will have access to the specimens.

Stool samples collected from consented participants will be shipped straight to [name] laboratory for microbiome analysis and storage. All samples will receive a designated study code. This code will be linked to the patient's data.

All samples, blood and stool, will be stored indefinitely for future research related to heart failure, GI bleeding, Omega-3 supplements, and microbiome.

STUDY TIMELINES

Each subject will actively participate in the study for 1 year after randomization. We will collect data from the subjects' medical records for an additional year. It will take approximately 6 months to enroll all study participants. Once the study is complete, it will take approximately 3 months to complete the primary analysis.

INCLUSION AND EXCLUSION CRITERIA

Inclusion Criteria

1. Subject has signed consent
2. Age ≥ 18 years
3. Subjects with a CF-LVAD or are scheduled to receive a CF-LVAD implant

Exclusion Criteria:

1. Psychiatric disorder or disease, irreversible cognitive dysfunction or psychosocial issues that might impair compliance with the study.
2. Patients already taking O3FA.

RECRUITMENT METHODS

Patients with advanced heart failure will be seen in clinic, in the cardiac catheterization laboratory, or inpatient wards or intensive care units. If the patient goes on to have an evaluation for LVAD during their clinical course, a member of the research team will approach the patient. We currently implant approximately 60 CF-LVAD per year at the University of

Chicago. Recruitment from the recently implanted cohort and newly implanted patients should provide us with sufficient patients for this study.

COMPENSATION FOR PARTICIPATION IN RESEARCH ACTIVITIES

There will be no compensation to participants in this study.

WITHDRAWAL OF PARTICIPANTS

Participants can be withdrawn without consent if they are not compliant with taking O3FA daily. They will be notified of withdrawal and all their data will be permanently erased. If participants decide to withdraw from the study, all of the O3FA will be returned to the research team, and the all of their data will be permanently erased.

RISKS TO PARTICIPANTS

There is a slight risk associated with vein punctures. We will make every effort to obtain the samples during a standard of care blood draw. If this is not possible, the risks associated with a blood draw include pain, dizziness, fainting, infection (rare), and redness. There is also a risk of loss of confidentiality, which will be minimized by efforts to secure the data.

POTENTIAL BENEFITS TO PARTICIPANTS

There will be no direct benefit to patient. We hope that the existence of this data will facilitate fundamental and significant research in advanced heart failure, ultimately benefitting patients in the future.

STATISTICAL ANALYSIS, DATA MANAGEMENT, AND CONFIDENTIALITY

Statistical analysis will be performed using SPSS Statistics 22 (SPSS Inc, Chicago, IL, USA). Variables with 2-tailed p value <0.05 will be considered significant. Clinical parameters and outcomes including rates of GI bleeding, angiogenesis-related biomarkers, inflammatory markers, and microbiome data will be compared between the O3FA and control groups, both among the primary and secondary prevention arms using unpaired t-test or Mann-Whitney U test as appropriate. A necessary patient number for each group is calculated as 26 (total 104) by power analysis with 0.05 of α , 0.8 of effect size, 0.8 of $1-\beta$.

A master list maintaining patient names and code numbers will be stored in locked files. A password-protected computer located in the heart failure main office will contain a database for data collected in this study. Case report forms (CRF's) will be generated and filled out for each subject enrolled in this study.

There is a risk of loss of confidentiality. If a patient agrees to participate, and signs an informed consent, a signed copy of the consent will be given to them, a copy placed in their record and then the data will be abstracted into an electronic database. The database will be within the Department of Medicine, Section of Cardiology. The data will be password protected and covered by all of the firewalls and security features of the Department of Medicine.

The investigators seek to minimize these risks by labeling the study related data and specimens with a study code. This study code will be linked with the patient's data. Only the investigators

and their designated staff will have access to the databases and the link between study code numbers and patient identifying information.

Data and samples may be utilized by faculties who have the proper IRB approval to do so, and whose study objective meets with the overall objective of this research.

We may share coded data and/or samples outside of the institution in collaboration efforts. An IRB amendment will be submitted to the IRB for review if this happens. Additionally, if NIH funding is obtained for any proposed study, it is possible that the PI will be required to provide a copy of coded data to the NIH for public use. In either case, direct patient identifiers will never be shared.

ECONOMIC BURDEN TO PARTICIPANTS

There will be no economic burden to the participants.

CONSENT PROCESS

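### At least 14 secondary comparisons are each judged at p<0.05, so improved inflammation can be declared from any one of six to eight markers in either prevention arm

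*Combined protocol and SAP*

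**What the plan says.** - Study Endpoints: "Secondary endpoints include rate of GIB and improvement in inflammatory markers". No inflammatory marker is singled out, and improvement is not defined.
- Procedures Involved, Blood Collection: "The inflammatory markers to be measured are Interleukin-6 (IL-6), Interleukin-8, Interleukin-18 (IL-18), sCD40L, soluble Fas ligand (sFASL), and TNF" (alpha), which makes six. The same section adds that "inflammatory markers (hs-CRP and ESR) will be collected as standard of care", which makes eight.
- Objectives, Aim 3: GI bleeding is assessed "in both the population without prior GI bleeding events, and the population with prior GI bleeding events".
- Statistical Analysis: groups are compared "both among the primary and secondary prevention arms using unpaired t-test or Mann-Whitney U test as appropriate", and "Variables with 2-tailed p value <0.05 will be considered significant".
- Blood is drawn at 3 months, 6 months and 1 year after baseline. No visit is named for the comparison.

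The documents contain no multiplicity adjustment, no order among the secondary endpoints and no link between them and the primary result. They do not label the secondary endpoints exploratory.

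**The concern.** Two secondary endpoints on paper become a family of separate tests once the marker list and the two prevention arms are counted. The significance rule applies to each test alone. One low p-value among six to eight markers, in either arm, is enough to report that inflammation improved. The GI bleeding rate, which is the subject of the trial's title, gets two chances of its own.

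This is separate from the choice of primary endpoint. Naming one primary angiogenesis marker would leave every secondary test at 5%. The two sets also touch: sCD40L is in both lists under Blood Collection, and the Background says "we will investigate the effect of O3FA on angiogenesis parameters (Ang-1, Ang-2, VEGF, TNF" (alpha), so TNF-alpha is an angiogenesis parameter there and an inflammatory marker later.

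**Working it through.** **The plan's own figure.** Statistical Analysis says "A necessary patient number for each group is calculated as 26 (total 104) by power analysis with 0.05 of" alpha, with effect size 0.8 and power 0.8. A two-sided two-sample t-test gives 25.5, so 26 per group and 26 × 4 = 104; power at 26 per group is 80.7%. The figure reproduces. It is for one comparison at 0.05 and makes no allowance for multiplicity.

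**Number of tests at one visit.**
- GI bleeding + 6 panel markers, 2 arms: (1 + 6) × 2 = 14.
- With hs-CRP and ESR: (1 + 8) × 2 = 18.
- Six markers at all three follow-up visits plus one bleeding test: (6 × 3 + 1) × 2 = 38.

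**Independent tests, no true effect.** P(at least one p<0.05) = 1 − 0.95^k.
- k = 14: 51.2%
- k = 18: 60.3%
- k = 38: 85.8%. This is an upper figure, because repeat visits in the same patients are correlated.
- GI bleeding alone in two arms, k = 2: 9.75%

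**Correlated tests.** The arms contain different patients, so they are taken as independent. Within an arm, k normal test statistics share a common correlation ρ, which is an assumption. Then

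P(arm) = 1 − ∫ [Φ((1.96 − √ρ·f)/√(1−ρ)) − Φ((−1.96 − √ρ·f)/√(1−ρ))]^k φ(f) df, and P(both arms) = 1 − (1 − P(arm))².

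If bleeding is instead independent of the markers, k counts markers only, and 1 − P(arm) is multiplied by 0.95.

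| Assumed ρ | 14 tests, bleeding correlated like the markers | 14 tests, bleeding independent of markers | One arm, 7 tests (all correlated) | 18 tests (all correlated) |
|---|---|---|---|---|
| 0 | 51% | 51% | 30% | 60% |
| 0.3 | 47% | 48% | 27% | 55% |
| 0.5 | 41% | 43% | 23% | 47% |
| 0.8 | 28% | 33% | 15% | 30% |

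**Without bleeding.** Six markers in two arms (12 tests) still give 46% at ρ = 0 and 26% at ρ = 0.8.

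**Results favouring omega-3 only.** Each test then carries 0.025. For 14 independent tests, 1 − 0.975^14 = 30%; at ρ = 0.8 with bleeding correlated like the markers it is 14%. A single test carries 2.5%.

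**The case against.** **The 5% is a per-variable level.** A reader might infer that the plan exceeds an error rate it promised. It does not: no familywise rate is stated, and any plan with two unadjusted tests would pass 5% overall. This stands. The figures above describe what the rule allows, not a breached commitment.

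**No single headline figure is supported.** A reader might settle on a mid-range value such as 40%. That needs a within-arm correlation of about 0.5 to 0.6, depending on how bleeding is treated, and the documents give none. Only the range can be defended.

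**Pooling the arms is a choice.** Primary and secondary prevention are separate questions in different patients, each with its own randomised groups. Counted per arm the figure is about 15-30%. This also stands, and the inflation remains.

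**No success rule is written.** A reader might infer that the trial intends to claim bleeding prevention from one secondary p-value in one arm, even if the primary fails. Nothing in the documents says so. They do call such a result significant, with nothing to qualify it.

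**Secondary endpoints in a mechanistic study of 120 patients are often treated as exploratory.** Formal control across them is partly convention. That defence would work if the plan used the label. Instead it applies the significance rule to every variable.

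**Conclusion.** The point holds. The rule covers at least 14 secondary tests at one visit, or 18 with hs-CRP and ESR. With no true effect, the chance of at least one significant result among the 14 is 51% under independence and roughly 28-48% for assumed correlations of 0.8 to 0.3. Within one arm it is about 15-30%. Use of all three follow-up visits raises these figures.

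The sizes assume that each test holds its 5% level, that the arms are independent, and that correlation within an arm is uniform. The conclusion does not depend on the exact correlation, since even the lowest two-arm figure is more than five times 5%. The documents do not establish a breach of a stated familywise rate, nor any one value within the range. What they do establish is that the inflammation endpoint can be declared met on any one of six to eight markers in either arm. This should be corrected; it affects what may be claimed, not how patients are treated.

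**What to change.** In Study Endpoints and Statistical Analysis:

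1. Confine the significance rule to a short named list: the primary endpoint once it is defined, the GI bleeding rate, and one pre-named inflammation measure. That measure may be a single marker, or a score averaging standardised log markers on a fixed list. Name one visit for it.
2. For each listed endpoint, say whether it is tested once, stratified by prevention arm, or separately in each arm with alpha split. One option is Holm across the listed secondary tests. With two stratified tests the smallest p-value is compared with 0.05/2 = 0.025; with two endpoints in each of two arms, with 0.05/4 = 0.0125.
3. Report every other single-marker and other-visit result as an exploratory estimate with a 95% confidence interval and no significance claim.

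Gating GI bleeding on the primary endpoint is optional, and cannot be run until the primary is defined. Without a gate, Holm controls error among the listed secondaries only.

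**Cost.** A few sentences; no new patients, samples or data. Single-marker results can no longer be called significant, and a score dilutes an effect confined to one marker. If the effect is shared the score gains power. Assume 0.5 SD on each of six markers and correlation 0.5: the score's effect size is 0.5/√((1 + 5 × 0.5)/6) = 0.65. At 30 v 30 its power is 70%, against 48% for one named marker and 22% for one marker at 0.05/6.

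The 70% is for a single ungated test at 0.05 and should be quoted only as such. Placed behind GI bleeding it would fall. The retrospective rates in the Background (0.077 ± 0.419 v 0.305 ± 0.847 events per year) give an effect size of 0.228/√((0.419² + 0.847²)/2) = 0.34 and t-test power of about 26% at 30 v 30. If the two tests were independent, power to reach and pass the score would be about 0.26 × 0.70 = 18%; positive dependence would raise it.

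### Controls are assigned no O3FA, but their use of it is restricted only at entry, exposure is not reported by group, and low-exposure patients can be erased from the O3FA group alone

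*Combined protocol and SAP*

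**What the plan says.** - **Comparator.** Under Objectives, patients in Aims 1a and 1b are "randomized to high-dose O3FA or none". The trial is open label.
- **Usual advice.** Study Intervention describes O3FA as an over-the-counter product and adds: "Heart failure patients are routinely instructed to take an O3FA supplement for heart health".
- **Restriction at entry.** Exclusion criterion 2 is "Patients already taking O3FA". It acts only at enrolment.
- **Background care.** Procedures Involved says that "all patients will receive guideline-directed medical therapy during the study period". O3FA is not mentioned there.
- **Recording.** "Record medical history and medications" is listed for all subjects at baseline and at the eight later visits, from 1.5 to 12 months. O3FA is not named in that item. "Study drug compliance check" is listed at the same eight follow-up visits, for O3FA subjects only.
- **Withdrawal.** "Participants can be withdrawn without consent if they are not compliant with taking O3FA daily". The next sentence is: "They will be notified of withdrawal and all their data will be permanently erased".
- **Analysis.** The statistical section compares clinical parameters, GI bleeding, biomarkers, inflammatory markers and microbiome data between groups within each prevention arm. It does not name O3FA exposure. It gives 26 patients per group as necessary; Procedures Involved plans 30.

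**The concern.** The protocol's own account of usual care recommends the product that controls are meant to go without, and the product can be bought without prescription. If some controls take it, and respond in the same direction as the average patient, the difference between groups shrinks while still being described as O3FA versus none. Dilution of this kind does not create a false positive. It makes a null result hard to read: without exposure figures, no effect cannot be told apart from too little difference in exposure.

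The withdrawal rule adds a problem on the other side. Non-compliance with O3FA can occur only in the group assigned to take it, so the rule can remove low-exposure patients from that group while controls have no counterpart. Once a patient's data are erased, the groups compared are no longer the groups randomised, and the exposure table cannot be completed.

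**Working it through.** **The plan's own figure.** Inputs from the statistical section: two-sided alpha 0.05, standardised effect d = 0.8, power 0.8. A two-sample t-test (noncentral t) needs 25.52 patients per group, rounded up to 26, which matches the plan. Power is 80.7% at 26 per group and 86.1% at the planned 30.

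**What can be learned about exposure from the plan as written**

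| Item | O3FA group | Control group |
|---|---|---|
| Current users excluded at entry | Yes | Yes |
| Medications recorded, 9 visits | Yes, O3FA not named | Yes, O3FA not named |
| Compliance check, 8 visits | Yes | Not listed |
| Rule on non-study O3FA after randomisation | None stated | None stated |
| Withdrawal and erasure for non-compliance | Possible | Does not apply |
| Exposure named in the analysis | No | No |

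**Illustrative dilution.** The documents give no uptake rate, dose or start time for controls, so both quantities below are assumptions. Let c be the share of controls taking O3FA from the start and f the share of the full effect that they get, in the same direction.

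- Mean difference = 0.8 × (1 − c·f)
- Control variance = 1 + c(1 − c)(0.8f)²
- Effective d = mean difference ÷ √[(1 + control variance)/2]

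Example with c = 0.10 and f = 1: the difference is 0.8 × 0.9 = 0.72; the control variance is 1 + 0.09 × 0.64 = 1.0576; the pooled SD is √(2.0576/2) = 1.014; d = 0.72/1.014 = 0.710. Power at 30 per group is 77.1%.

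| Share of full effect (f) | Power at c = 10% | Power at c = 25% | Uptake at which power reaches 80% |
|---|---|---|---|
| 1 | 77.1% | 60.2% | 7.1% |
| 0.5 | 82.2% | 75.4% | 15.2% |
| 0.25 | 84.3% | 81.4% | 31.4% |

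The last column is where the effective d falls to 0.736, the value that gives 80% power with 30 per group. At full effect, 2 of 30 controls leaves 80.4% and 3 of 30 leaves 77.1%. Holding the SD at 1 instead of widening it for a mixed control group gives 78% at c = 10%, f = 1, so the choice of variance matters little.

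These figures describe one continuous outcome at d = 0.8 within one prevention arm. They do not apply to GI bleeding or the microbiome.

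**The case against.** The strongest reply is that the route to contamination is inferred. The sentence on routine advice describes heart failure patients in general and sits beside text on funding and storing the supplement. Open-label assignment to no O3FA could fairly be read as displacing that advice, and any instruction to controls might sit in the consent form, which is not among the documents. Exclusion 2 leaves patients who were not taking O3FA at entry, so later uptake may be low. Medications are recorded for everyone at nine visits, and staff would have reason to note the study agent. Clinical parameters, in the analysis section, could be stretched to cover it. A comparator that allows usual advice is also legitimate, so suspending the advice is partly a matter of preference.

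Most of this stands, and it limits the point. A reader might infer that controls will take O3FA, that their use goes unrecorded, or that power falls to 60%. The documents support none of these. No uptake rate is given; the medication record covers both groups; and the 60% figure needs a quarter of controls, all non-users at entry, to get the full effect from the start, which would take a dose near 4,000 mg a day. Lower doses or later starts dilute less.

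Two things survive. The protocol text makes no commitment to identify or report O3FA exposure by group. And the withdrawal rule is explicit and can act on one group only. It concerns loss from the O3FA group rather than uptake in controls, but it bears on the same question: what difference in exposure the comparison represents.

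**Conclusion.** The point holds, as a minor one. In the supplied protocol text, O3FA use by controls is restricted only at entry, while the same text says the product is routinely advised. Control uptake of unknown and possibly low size could dilute a true effect, provided users respond in the same direction as the average. With 30 per group, power for a marker stays at about 80% or more up to about 7% uptake at full effect or 15% at half effect; both inputs are assumed, so this is illustration and not a forecast. The part that needs no assumed uptake is that exposure is not planned to be reported, and that any use of the withdrawal and erasure rule would rule out both an as-randomised comparison and a complete exposure table. The conclusion is limited to the protocol text, since case report forms and consent pages were not available.

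**What to change.** 1. **Record.** At the nine existing medication reviews, record non-study O3FA in both groups (yes/no, product, daily mg). At the eight existing compliance checks, record study pills taken since the last visit (4,000 mg as 4 pills implies 4,000/4 = 1,000 mg per pill).
2. **Report.** Beside the primary result, by group within each prevention arm, give the percentage using non-study O3FA and the mean daily O3FA dose from randomisation to each blood draw (3, 6 and 12 months).
3. **Analyse and retain.** Analyse patients as randomised. Do not withdraw controls for taking O3FA. Amend the withdrawal section so that non-compliant subjects stay in follow-up and their data are kept, and so that data collected before a voluntary withdrawal are kept where consent allows.
4. **Define the comparator.** Either ask controls not to start O3FA during the 1-year study period except for a documented specific indication, if the IRB agrees, or describe the comparator as *no study-supplied O3FA, usual advice allowed*.

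The cost is one case report form line, a pill count, one descriptive table and short protocol amendments; no new visits, assays or patients are needed. If the advice is suspended, controls forgo a routinely advised supplement for a year, which needs IRB agreement. Items 1 to 3 apply whichever option is taken. The second year of record review has no study visits, so exposure in that year stays outside this fix.
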